13.2 Data Analysis Plan

The primary and first secondary analyses will include all 16 eligible and treated patients with completed ¹⁸F-fluciclovine-PET/CT scans and pathology dissection. Among these 16 patients, those who undergo cystectomy will be included for secondary analysis 2 and 3.

We will tabulate the metastatic disease status by ¹⁸F-fluciclovine-PET/CT (limited to bladder, locoregional nodes positive, or distant) and pathologic stage at radical cystectomy and compute the agreement rate, along with the corresponding 90% exact binomial confidence interval (CI). The proportion of patients who show positive ¹⁸F-fluciclovine-PET/CT will be computed, along with the corresponding 90% exact binomial confidence interval. This similar methodology will be used to evaluate the proportion of agreement compared to histopathology and the rates of locoregional disease and suspected distant metastatic disease detected by ¹⁸F-fluciclovine-PET/CT. In addition, treating pathologic and/or biopsy findings as the reference standard, we will estimate the sensitivity and specificity of ¹⁸F-fluciclovine-PET/CT for detection of metastatic disease.

The analysis of the relationship of ¹⁸F-fluciclovine uptake on PET/CT (SUVmax) in primary bladder tumor to pathologic tumor grade/size after radical cystectomy will be analyzed using the Kruskal-Wallis test. The Wilcoxon-Rank-Sum test will be used to assess the association between SUVmax and the presence/absence of ASCT2 and LAT1 amino acid transporters in the resected primary bladder tumors.

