13.6 Analysis of Secondary Endpoints

Secondary objectives are to:

1. To determine the rate of detection of suspected distant metastatic disease by ¹⁸F-fluciclovine-PET/CT in patients with cT2-T4N0M0 muscle invasive bladder cancer by conventional CT/MRI imaging.

Endpoints:

- 1) Visualization and number of distant metastases on ¹⁸F-fluciclovine-PET/CT

Visualization of distant metastases on ¹⁸F-fluciclovine-PET/CT will be binary-categorized as present/absent. In the categorization, a qualitative scale (0-4) may be accounted and an optimal cut-off may be examined. We will compute sensitivity to compare ¹⁸F-fluciclovine-PET/CT with standard imaging modalities for distant metastases. The number of distant metastases will be descriptively shown by imaging modalities.

2. To correlate ¹⁸F-fluciclovine uptake on PET/CT in primary bladder tumor with pathologic primary tumor stage and size after radical cystectomy.

Endpoints:

- ¹⁸F-fluciclovine SUVmax in primary bladder tumor
- Primary tumor stage and size at radical cystectomy

The amount of ¹⁸F-fluciclovine accumulation in the primary bladder tumor on PET will be quantified using the maximum standardized uptake value (SUVmax). Tumor grade will be assessed histopathologically with specimens from cystectomy as part of standard-of-care. The correlations between ¹⁸F-fluciclovine uptake and tumor grade will be evaluated using Spearman correlation coefficients.

3. To correlate ¹⁸F-fluciclovine uptake on PET/CT to the presence/absence of ASCT2 and LAT1 amino acid transporters in the resected primary bladder tumors.

Endpoints:

- ¹⁸F-fluciclovine SUVmax in primary bladder tumor
- Presence/absence of ASCT2 and LAT1 amino acid transporter in resected primary bladder tumors

The Wilcoxon-Rank-Sum test will be used to assess the association between SUVmax and the presence/absence of a ASCT2 and LAT1 amino acid transporters in the resected primary bladder tumors.

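### Sections 13.2 and 13.6 name different methods (Kruskal-Wallis and Spearman) for the same SUVmax-grade association, and neither is said to govern

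*Combined protocol and SAP*

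**What the plan says.** Secondary objective 2 relates fluciclovine uptake in the primary bladder tumour to pathology at cystectomy.

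- Section 13.2 states that the relationship of SUVmax "in primary bladder tumor to pathologic tumor grade/size after radical cystectomy will be analyzed using the Kruskal-Wallis test".
- Section 13.6, under the same objective, states that the correlations between "uptake and tumor grade will be evaluated using Spearman correlation coefficients".
- Section 13.6 lists as the pathologic endpoint "Primary tumor stage and size at radical cystectomy", and Section 1.3.2 also names stage and size. Sections 13.1 and 13.2 say grade and size, and the method sentence in 13.6 says grade.
- For objective 3 the two sections agree: "The Wilcoxon-Rank-Sum test will be used to assess the association between SUVmax and the presence/absence of ASCT2 and LAT1 amino acid transporters" (13.2).
- On numbers, 13.2 says: "Among these 16 patients, those who undergo cystectomy will be included for secondary analysis 2 and 3". The maximum is therefore 16 tumours.

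No significance level is given for any of these analyses. The only error rate in the document, one-sided 0.101 in Section 13.3, belongs to the primary two-stage rule.

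**The concern.** Two unconditional method statements for one association leave the choice to the analyst, who may make it after seeing the data. The methods ask different questions. Kruskal-Wallis asks whether SUVmax differs in any way between groups and ignores their order; Spearman asks whether SUVmax rises or falls with the ordered variable. In at most 16 tumours, a borderline result can be significant under one and not under the other.

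Two related gaps sit in the same sentences. Kruskal-Wallis needs groups, but no grouping of tumour size is defined, and 13.6 lists size without giving it a method. Stage is the named endpoint, but neither method sentence mentions it.

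What is at stake is how a named secondary objective is reported. The agreement rate and its decision rule are not touched.

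**Working it through.** **Plan's own figures.** The plan gives none for these tests. Its only design figures are for the primary rule in 13.3, and they reproduce by exact binomial calculation. The probability of early stopping at 50% agreement is P(X ≤ 5 of 10) = 638/1024 = 0.623 (stated 0.62). One-sided type I error is 0.1012 (0.101), power is 0.79995 (79.9%), and the 90% exact interval for 12/16 is 0.516 to 0.910 (0.52, 0.91).

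**The method text side by side.**

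| Pathologic variable | Section 13.2 | Section 13.6 |
|---|---|---|
| Grade | Kruskal-Wallis | Spearman |
| Size | Kruskal-Wallis, no groups defined | endpoint listed, no method |
| Stage | not mentioned | endpoint listed, no method |
| ASCT2, LAT1 | Wilcoxon rank-sum | Wilcoxon rank-sum |

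Only grade has two competing methods.

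**Two levels.** Here the Kruskal-Wallis statistic is H = (n−1)r², where r is Spearman's coefficient, so the tests differ only in their reference distribution. At n=16 and two-sided 0.05:

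- Kruskal-Wallis rejects when 15r² > 3.841, that is |r| > 0.506.
- Spearman (t with 14 degrees of freedom, critical value 2.145) rejects when |r| > 2.145/√(14 + 2.145²) = 0.497.

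Attainable values are |r| = d/√(340·m(16−m)/16), where m is the size of one group and d is the distance of its rank sum from expectation.

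- For an 8/8 split the denominator is √1360 = 36.88. The neighbouring values are 18/36.88 = 0.488 and 19/36.88 = 0.515. None falls between the cut-offs, so the decisions are identical.
- For a 3/13 split the denominator is √828.75 = 28.79, and 14.5/28.79 = 0.504 does fall between them. Simulated disagreement is 2% under no association and 7% under an assumed shift of 1.2 SD.

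**Three and four levels.** Kruskal-Wallis spends k−1 degrees of freedom on k groups; Spearman spends one. Simulation assumptions: n=16, normal SUVmax with correlation 0.5 to a latent pathologic variable, that variable cut into near-equal ordered groups, level 0.05.

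| Levels | Kruskal-Wallis power | Spearman power | Tests disagree |
|---|---|---|---|
| 2 (equal) | 0.32 | 0.32 | 0% |
| 3 | 0.26 | 0.41 | 19% |
| 4 | 0.20 | 0.43 | 27% |

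A differently specified trend points the same way. A shift of 0.7 SD per level over three groups gives 0.38 against 0.56 with 22% disagreement. A shift of 0.5 SD per level over four groups gives 0.26 against 0.52 with 30%. With no true association the two disagree in 5 to 6% of trials.

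**Size.** With the same latent correlation of 0.5, Spearman on size as measured has power about 0.46. Kruskal-Wallis on thirds or halves has 0.25 to 0.32.

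**Multiplicity, for scale.** Following 13.6 alone gives three tests, 13.2 alone gives four, and both together give five. At an assumed 0.05 with independent tests, the chance of at least one false positive is 1 − 0.95³ = 0.143, 1 − 0.95⁴ = 0.185 and 1 − 0.95⁵ = 0.226. One simulation with a shared SUVmax, varying the correlation among the pathologic variables from 0.8 to 0, gives 0.146 to 0.170 for four tests and 0.167 to 0.198 for five. The second grade test therefore adds 0.021 to 0.028.

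**The case against.** Several points on the other side are sound.

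- Section 13.6 speaks of correlation coefficients and mentions no test or p-value. It can be read as a descriptive estimate beside the test in 13.2. That reading is possible, but neither section says so, and both give their method as the analysis of the same association.
- The number of grade levels is never stated, and with two equal levels there is no conflict in practice. That stands as a condition on the finding. The objective and endpoint name stage, however, and eligibility covers cT2 to T4, so three or more ordered levels are realistic.
- Kruskal-Wallis is weaker only against ordered alternatives and would do better against a non-monotone pattern. That is true, and it is the price of the proposed choice.
- This is a pilot, objective 2 is framed as investigating a relationship, and the only success rule is 11 of 16 agreements. That limits the weight of the point.

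A reader might go further and infer that unadjusted testing of one SUVmax variable makes a reported false association likely. The figures do not support that: the chance is roughly 15 to 20% at an assumed 0.05. It would take about 14 independent tests at that level to pass one half (ln 0.5/ln 0.95 = 13.5). Even five tests at an assumed 0.10 simulate at no more than 0.36.

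A reader might also infer that two tests are prescribed whether stage or grade is meant. Both method sentences name grade only; stage has no method at all.

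**Conclusion.** The contradiction is real and is not resolved elsewhere in the document. It concerns two stated rules, not a missing detail. Its effect is conditional. With three or four ordered levels, a true monotone association of latent correlation 0.5 and a 0.05 level, the choice of section changes the significance call in about one trial in five to one in four, and Kruskal-Wallis gives up about 0.15 to 0.23 of power (0.41 − 0.26; 0.43 − 0.20). With two equal levels it has no effect. The correlation, the level, the group sizes and the number of levels are assumptions, because the plan states none of them.

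The undefined size groups and the stage/grade mismatch belong to the same correction. Multiplicity is a side issue: the conflict itself adds only 2 to 3 percentage points, and no decision in the study depends on these tests. This is a worthwhile correction to a secondary analysis, not a threat to the study's conclusion.

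**What to change.** Before the analysis:

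1. Delete the Kruskal-Wallis sentence in 13.2.
2. In both 13.2 and 13.6, name Spearman's rank correlation as the single method for SUVmax against the ordered pathologic variable and against tumour size as measured, without grouping.
3. In the same edit, make that variable the one in the stated objective and endpoint (stage, with size, as in 1.3.2 and the 13.6 list), and bring 13.1, 13.2 and the 13.6 analysis text into line.
4. Keep one Wilcoxon rank-sum test each for ASCT2 and LAT1.

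The cost is wording only, with no extra patients or data. The one statistical downside is that Spearman is less sensitive to non-monotone differences. A sentence labelling objectives 2 and 3 as exploratory would be good practice but is optional.

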13.3 Sample Size, Accrual Rate and Study Duration

The planned sample size is 16 participants with completed ¹⁸F-fluciclovine-PET/CT scans and pathology dissection. Patients who did not complete the scans or without pathology dissection are unevaluable and will be replaced. Considering 4 patients who may be unevaluable and replaced, up to 20 patients can be enrolled. The estimated accrual rate is 1 participant/month, and accrual is expected to complete in another 16 months. Participants who undergo ¹⁸F-fluciclovine-PET/CT but have altered surgical plans due to clinical findings during surgery may remain evaluable and not replaced if a lymph node dissection was performed as determined by the study investigators. This will not affect the primary study objective given the primary objective is the agreement rate between PET/CT and pathology for metastases. Participants who do not undergo cystectomy will not be included for secondary objectives (2 and 3).

We will employ a Simon's 2-stage design to test the hypothesis that the agreement rate of metastatic disease status between ¹⁸F-fluciclovine-PET/CT and histopathology will be 75%, compared to a null agreement rate of 50%. In the first stage we will enroll 10 patients, and if 6 or more scans among those 10 are in agreement regarding metastatic disease status, we will open the second stage of accrual to enroll an additional 6 patients, making a total sample size of 16 patients. If fewer than 6 scans are in agreement in the first stage then the study may be stopped or the study design may be amended to enroll additional patients. In order to consider the study a success, a total of 11 or more scans need to be in agreement among all 16 scans. This design has a 0.62 probability of stopping early under the null, and has 79.9% power while maintaining an overall one-sided type I error rate of 0.101. The agreement rate between ¹⁸F-fluciclovine-PET/CT and histopathology is expected to be 75% (or higher) and the corresponding 90% CI will be (0.52, 0.91).

| Accrual Targets | | | |
|---|------------|--------|-------|
| Ethnic Category | Sex/Gender | | |
| | Females | Males | Total |
| Hispanic or Latino | + | = | = |
| Not Hispanic or Latino | + | = | = |
| Ethnic Category: Total of all subjects | (A1) + | (B1) = | (C1) |
| Racial Category | | | |
| American Indian or Alaskan Native | + | = | = |
| Asian | + | = | = |
| Black or African American | + | = | = |
| Native Hawaiian or other Pacific Islander | + | = | = |
| White | + | = | = |

| Racial Category: Total of all subjects | (A2) | + | (B2) | = | (C2) |
|--|-----------|---|-----------|---|-----------|
| | (A1 = A2) | | (B1 = B2) | | (C1 = C2) |

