5.3 Surgery

After completion of the ¹⁸F-fluciclovine-PET/CT scan, participants will undergo standard-of-care radical cystectomy surgery as determined by medical oncology and urology. If surgical plans (for example, the presence of unsuspected extensive disease precluding cystectomy) are altered based on clinical findings during surgery, the patient may remain evaluable if a lymph node dissection is performed as determined by the study team. Results from the standard-of-care evaluation of the pathologic specimens will be collected and reviewed. This includes evaluation of pathological samples for metastatic cancer burden.

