5.7 Criteria for Taking a Participant Off Study

Participants will be removed from study when any of the following criteria apply:

- Lost to follow-up
- Withdrawal of consent for data submission
- Death

The reason for taking a participant off study, and the date the participant was removed, must be documented in the case report form (CRF). In addition, the study team will ensure Off Treatment/Off Study information is updated in OnCore in accordance with DF/HCC policy REGIST-101. If a participant is taken off study prior to undergoing the research ¹⁸F-fluciclovine-PET/CT scan, the participant may be replaced.

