13. STATISTICAL CONSIDERATIONS

13.1 Study Design, Objectives, and Endpoints

This is a prospective pilot study evaluating ¹⁸F-fluciclovine-PET/CT for detecting metastatic disease in patients with cT2-T4N0M0 muscle invasive bladder cancer.

The primary objective of this study is to estimate the agreement rate of metastatic disease status between ¹⁸F-fluciclovine-PET/CT and histopathology from radical cystectomy for detecting

locoregional metastatic disease in patients with cT2-T4N0M0 muscle invasive bladder cancer by conventional CT/MRI imaging. Secondary objectives include estimating of the rate of detection of suspected distant metastatic disease by ¹⁸F-fluciclovine-PET/CT, analysis of the association of ¹⁸F-fluciclovine uptake on PE/CT in primary bladder tumor with pathologic tumor grade/size after radical cystectomy, and analysis of ¹⁸F-fluciclovine uptake on PET/CT to the presence/absence of ASCT2 and LAT1 amino acid transporters in the resected primary bladder tumors.

The primary endpoints are metastatic disease status by ¹⁸F-fluciclovine-PET/CT and pathologic stage at radical cystectomy. The agreement rate is defined as the number of scans that are considered positive metastatic disease by both ¹⁸F-fluciclovine-PET/CT and histopathology and those considered negative metastatic disease by both ¹⁸F-fluciclovine-PET/CT and histopathology, out of all scans performed. A positive ¹⁸F-fluciclovine-PET/CT is defined as evidence of metastatic disease either regionally in the pelvic lymph nodes or distantly to bone, lungs, viscera, or lymph nodes outside of the pelvis. The ability of ¹⁸F-fluciclovine-PET/CT for detecting locoregional metastatic disease will be defined as the presence of disease detected locoregionally on ¹⁸F-fluciclovine-PET/CT. Secondary endpoints include visualization (present/absent) and number of distant metastases on ¹⁸F-fluciclovine-PET/CT. The amount of ¹⁸F-fluciclovine accumulation in the primary bladder tumor on PET will be quantified using the maximum standardized uptake value (SUVmax). Tumor grade/size and the presence of amino acid transporters will be assessed histopathologically with specimens from cystectomy as part of standard-of-care.

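### Scanned participants without a dissection are replaced and left out of the analysis, although agreement is defined over all scans; if the loss depends on the PET read, accuracy estimates are distorted

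*Combined protocol and SAP*

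**What the plan says.** The plan describes in several places who counts towards the primary endpoint.

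- **13.3:** "Patients who did not complete the scans or without pathology dissection are unevaluable and will be replaced". A completed scan does not protect a participant from replacement. The allowance is stated as "Considering 4 patients who may be unevaluable and replaced, up to 20 patients can be enrolled".
- **13.3, exception:** participants whose surgical plan changes because of findings during surgery "may remain evaluable and not replaced if a lymph node dissection was performed as determined by the study investigators". Section 5.3 says the same. Surgery cancelled beforehand is not covered.
- **13.2:** "The primary and first secondary analyses will include all 16 eligible and treated patients", meaning those with a completed scan and a dissection. For sensitivity and specificity it goes further, "treating pathologic and/or biopsy findings as the reference standard".
- **13.1:** the agreement rate is the number of concordant scans "out of all scans performed".
- **13.7.2:** evaluability for the primary endpoint requires the scan and radical cystectomy.
- **5.7:** replacement is mentioned once, in a sentence that begins "If a participant is taken off study prior to undergoing the research" scan.

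Section 5.1 places the scan before surgery and leaves surgery to standard of care. No section says whether the treating team sees the PET read. No bound, sensitivity analysis or separate listing is planned for scanned participants without a dissection.

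**The concern.** There are two linked problems.

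The first is on the page. A participant who is scanned but never has nodes dissected is in the denominator under 13.1 and out of it under 13.2 and 13.3. A participant with a dissection but no cystectomy is in under 13.3 and out under 13.7.2. Two analysts following different sections could report different primary results.

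The second is conditional. Agreement can be scored only where histology exists, so the 16 are a verified subset of those scanned. If a positive read makes dissection less likely, the subset is selected on the index test and the usual partial verification bias follows. The question arises most for scans positive for distant disease, which 13.1 counts as PET-positive. The first secondary endpoint, the rate of suspected distant disease, is exposed as well: it needs no dissection, yet 13.2 restricts it to the same 16. The stated type I error and power also assume that the 16 are not selected by PET result.

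**Working it through.** **1. The plan's own figures (13.3).** The rule is to continue at 6 or more of 10 and declare success at 11 or more of 16, testing 50% against 75%.

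- P(early stop | 0.50) = P(X ≤ 5 | n = 10) = 0.623 (stated 0.62).
- P(success | p) = Σ over x = 6..10 of b(x; 10, p) × P(Y ≥ 11 − x | n = 6, p). This gives 0.101 at p = 0.50 (stated 0.101) and 0.800 at p = 0.75 (stated 79.9%).
- Exact 90% CI for 12/16: 0.516 to 0.910 (stated 0.52 to 0.91).

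The design arithmetic is sound.

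**2. Inputs for the selection check.** Prevalence of nodal metastasis is 30% (section 2.1). Sensitivity (Se), specificity (Sp) and the share *d* of PET-positives who lose their dissection are not in the documents. They are assumptions, and no PET-negative patient is assumed lost.

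**3. Formulas.** With prevalence π: TP = π·Se·(1−d), FN = π·(1−Se), FP = (1−π)·(1−Sp)·(1−d), TN = (1−π)·Sp, and T is their sum. Apparent Se = TP/(TP+FN), apparent Sp = TN/(TN+FP), agreement = (TP+TN)/T. Expected scans for 16 evaluable = 16/T.

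**4. A quarter of PET-positives lost (d = 0.25).**

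- True 0.60/0.90: TP 0.135, FN 0.12, FP 0.0525, TN 0.63, T 0.9375. Apparent Se = 0.135/0.255 = 0.53; Sp = 0.63/0.6825 = 0.92; agreement = 0.765/0.9375 = 0.816, against a true 0.18 + 0.63 = 0.81.
- True 0.50/0.50: TP 0.1125, FN 0.15, FP 0.2625, TN 0.35, T 0.875. Apparent Se = 0.1125/0.2625 = 0.43; Sp = 0.35/0.6125 = 0.57; agreement = 0.4625/0.875 = 0.529, against a true 0.50.

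**5. Range, at 30% prevalence.** P(success) puts the agreement through the two-stage rule in step 1.

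| True Se/Sp | d | Apparent Se/Sp | Agreement | P(success) | Scans per 16 |
|---|---|---|---|---|---|
| 0.60/0.90 | 0 | 0.60/0.90 | 0.810 | 0.928 | 16.0 |
| 0.60/0.90 | 0.25 | 0.53/0.92 | 0.816 | 0.936 | 17.1 |
| 0.60/0.90 | 0.50 | 0.43/0.95 | 0.823 | 0.946 | 18.3 |
| 0.75/0.75 | 0.25 | 0.69/0.80 | 0.771 | 0.852 | 17.8 |
| 0.75/0.75 | 0.50 | 0.60/0.86 | 0.797 | 0.906 | 20.0 |
| 0.50/0.50 | 0.25 | 0.43/0.57 | 0.529 | 0.148 | 18.3 |
| 0.50/0.50 | 0.50 | 0.33/0.67 | 0.567 | 0.230 | 21.3 |

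The last row needs more scans on average than the cap of 20 enrolled, so it is an outer limit.

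**6. Direction.** When loss depends only on the PET read, Se can only fall and Sp can only rise. Agreement is an average of the positive predictive value (PPV) and the negative predictive value (NPV), so dropping positives raises it when PPV < NPV and lowers it otherwise. At 30% and 0.60/0.90, PPV = 0.18/0.25 = 0.72 and NPV = 0.63/0.75 = 0.84, so it rises. At an assumed 40% prevalence and 0.50/0.90, PPV = 0.20/0.26 = 0.77 and NPV = 0.54/0.74 = 0.73; agreement falls from 0.740 to 0.736 at d = 0.50.

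**7. Bounds without any bias model.** If all four replaced participants had been scanned, 11/16 (0.69) corresponds to between 11/20 = 0.55 (90% CI 0.35 to 0.74) and 15/20 = 0.75 (0.54 to 0.90).

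**The case against.** A reader might infer that the plan has an established verification bias because positive scans will cancel surgery. The documents do not support that. Section 3.1.3 requires cystectomy to be planned already, and 5.1 expects it to follow the scan. The benefits of pre-operative detection listed in 2.1 are risk stratification, tailoring neoadjuvant therapy and tailoring the extent of node dissection; cancelling cystectomy is not among them. Diversion remains possible because masking is not stated, but no figure for it exists.

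A reader might also infer that sensitivity is always biased down and specificity up. That holds only for loss driven by the PET read. Loss because disease proves unresectable at surgery has no fixed direction: if only node-positive patients are lost, specificity is unchanged, and if that loss is unrelated to the PET read, so is sensitivity.

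Nor does 5.7 flatly contradict 13.3. It permits replacement before the scan without saying that this is the only ground, and it has off-study reasons recorded in the case report form. Such patients are absent from the 6/10 and 11/16 counts, not from the records.

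Two further points carry weight. Some replacement is unavoidable, since agreement needs histology. And the effect on the primary endpoint can be trivial: about one percentage point at 0.60/0.90, against a planned interval of 0.52 to 0.91. The allowance of four also covers incomplete scans, so four scanned losses is the extreme.

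What remains is the clash between 13.1, 13.2/13.3 and 13.7.2, and the lack of any planned account of scanned participants without dissection.

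**Conclusion.** The point holds as an unreconciled evaluability rule and denominator, with a conditional risk of selection on the PET result. The conflict between sections needs no assumption. The size of any bias rests on assumed accuracy and an assumed share of PET-positives lost. With a quarter lost at 30% prevalence, sensitivity drops by about 0.07 in both scenarios of step 4. The change in agreement runs from under 0.01 (true 0.60/0.90) to about 0.03 (true 0.50/0.50), the latter lifting false success from 0.101 to 0.148. If the read is masked until surgery, this route closes but the conflict between sections stays. The matter should be corrected; it does not invalidate the design, whose stated operating characteristics reproduce.

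**What to change.** 1. Reconcile 5.7, 13.1, 13.2, 13.3 and 13.7.2 on one evaluable set and one denominator, and state whether the PET read is withheld until surgery.
2. Keep the 16 verified patients for the 6/10 and 11/16 rules, so the design's error rates need no recalculation.
3. In the primary table, add a separate row for every scanned participant without dissection, with the PET read and the reason. Report agreement with best-case and worst-case bounds over all scanned participants, as in step 7.
4. Report the distant-detection rate (secondary objective 1) in all scanned participants.
5. Use routine-care biopsy results only in the sensitivity and specificity estimate, where 13.2 already accepts them. Keep them out of the primary count: its reference is cystectomy histopathology, and routine biopsies would mostly follow positive scans and so add confirmed positives selectively.

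Replacement should not hinge on a judgement, made after the scan, of whether the reason was related to the PET result; listing all cases avoids that. The cost is wording, one extra table and a wider reported range when patients are lost. No extra patients or procedures are needed.
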